#### 2.2 Trial Design

[figure not shown]
This is a Phase II, multi-center, open label, single dose study in patients with tumor types known to overexpress GRPR, including breast, prostate, colorectal, non-small cell and small-cell lung cancer.

Population will be divided in two groups:

• Phase-II dosimetry group: 10 patients bearing breast (n=5 female patients) and prostate cancer (n=5 male patients) will undergo additional assessments to confirm previous data on tracer bio-distribution, radiation dosimetry, residence time for critical organs, and absorbed dose critical organs for [Ga]-NeoBOMB1. Patients enrolled in the dosimetry group in France will be relapsed or refractory breast and prostate cancer. Serial venous whole blood and urine samples will be collected for activity-based pharmacokinetic characterization. Patients will undergo 4 15-min-static whole-body PET scans at 15 min, 1h±15 min, 2h±15 min and 4h±30 min post injection (p.i.) to determine absorbed doses to normal organs and to target tumor lesions. Venous whole blood samples will be collected at pre-dose (0), 5, 10, 20, 30±5, 60±5 min, and at 2h±10 min and 3-4 h±10 min p.i. Urine samples at pre-dose, from 0-2 h and from 2-4 h p.i. will also be collected.

• **Phase-II non-dosimetry group:** 40 patients bearing breast cancer (n=5), prostate cancer (n=5), colorectal cancer (n=10), NSCLC (n=10), SCLC (n=10). PET-imaging will be reduced to 2 whole body scans at 1h30±30min and at 2h30±30min likely to be a 15-min static late PET for all tumor-types. Only prostate tumor patients will undergo an additional early 5-min static PET scan to better assess lymph node metastases (if applicable). Blood and urine sampling will be omitted.

GRPR expression must be assessed while the study is ongoing within 4 weeks after IMP injection by Immunohistochemistry staining from archival or recent biopsy specimens (not older than 6 months prior to IMP injection).

All study objectives, with the exception of the secondary one relative to bio-distribution and dosimetry that will be assessed only within the dosimetry group, will be assessed in the overall population (n=50). Analyses of the dosimetry group data will lead to the optimal time window for PET/CT imaging for future clinical trials. However, in the case that the Sponsor obtains the results of the dosimetry and bio-distribution assessments from at least 3 patients of the dosimetry group before the full completion of the study recruitment and the results show that the optimal time window is different from 1h30 $\pm$ 30min or 2h30 $\pm$ 30min as initially predicted by the Sponsor, the time points of the whole-body PET/CT scans for the remaining patients included in the non-dosimetry group will be adjusted.

#### 2.3 Study Assessments

For the detailed schedule of expected events and study procedures to be conducted at each visit and time point, please refer to Section 4.5 in the protocol. The schedule of assessments for dosimetry group is different from that of non-dosimetry group due to one additional study objective pertaining to the bio-distribution and dosimetry.

#### **3** STUDY ENDPOINTS

#### 3.1 Primary Study Endpoints

- Number and location of tumor lesions detected by [Ga]-NeoBOMB1 overall and for each tumor type
- Calculation of the ratio tumor/background SUV and %ID/g and calculation of absorbed dose (uGy/MBq) in tumor overall and for each tumor type

#### 3.2 Secondary Study Endpoints

- Standard safety parameters (clinical monitoring, laboratory, and ECG)
- Tolerability and safety of the administration of a diagnostic dose of [Ga]-NeoBOMB1 in patients with malignancies known to overexpress GRPR as determined by absence of:
  - increased number of SAEs compared to other peptide-based radiotracers;
  - clinically relevant changes of physiological parameters (blood pressure, heart rate, and ECG findings)
- Generation of decay corrected tissue time-activity curves (TACs) from [Ga]-NeoBOMB1 PET/CT images in normal organs and tumor lesions.
- Quantification of urinary excretion of [Ga]-NeoBOMB1
- Calculation of half-life of [Ga]-NeoBOMB1 in blood
- Generation of non-decay-corrected TACs from [Ga]-NeoBOMB1 PET/CT images in normal organs and tumor lesions
- Calculation of residence times in critical organs and tumor lesions of [Ga]-NeoBOMB1
- Calculation of absorbed doses in critical organs and effective whole body dose of [Ga]-NeoBOMB1
- Calculation of pharmacokinetic (PK) parameters, such as maximum concentration observed (*Cmax*), time of maximum observed drug concentration occurrence (*tmax*), area under the concentration-time curve from time zero (pre-dose) to some fixed time t [*AUC(o-t)*], AUC(0-t) divided by the dose administered [*AUC(o-t)*/D], half-life (*t*1/2), area under the concentration-time curve from time zero (pre-dose) extrapolated to infinite time [*AUC(o-tinf)*], total systemic clearance for intravenous administration (CL), the apparent volume of distribution of the parent test item in the test system (Vd)
- Number and location of tumor lesion detected by [Ga]-NeoBOMB1 in comparison with comparable standard imaging modalities such as FDG-PET
- Calculation of the [Ga]-NeoBOMB1 PET overall, positive and negative agreement on a lesion-by-lesion basis as well as on a patient basis relative to the standard imaging overall and for each tumor type
- Comparison of number of patients with tumor lesions detected by [Ga]-NeoBOMB1 with cytology and/or histopathology from archival and/or recent biopsy specimens

• Calculation of the [Ga]-NeoBOMB1 PET sensitivity and specificity on a lesion-by-lesion basis for all lesions with associated biopsy data, and on a patient basis relative to histopathology / cytology data

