# 3.3 Study Endpoints

- 3.3.1 Primary Study Endpoint
  - Number and location of tumour lesions detected by [Ga]-NeoBOMB1 overall and for each tumour type
  - Calculation of the ratio tumour/background SUV and calculation of percentage absorbed dose in tumour overall and for each tumour type.
- 3.3.2 Secondary Study Endpoints
  - Standard safety parameters (clinical monitoring, laboratory, ECG)
  - Tolerability and safety of the administration of a diagnostic dose of [Ga]-NeoBOMB1 in patients with malignancies known to overexpress GRPR as determined by absence of:
    - increased number of SAEs compared to other peptide-based radiotracers;
    - clinically relevant changes of physiological parameters (blood pressure, heart rate, ECG findings)
  - Generation of decay corrected tissue TACs from [Ga]-NeoBOMB1 PET/CT images in normal organs, tumour lesions.
  - Quantification of urinary excretion of [Ga]-NeoBOMB1
  - Calculation of half-life of [Ga]-NeoBOMB1 in blood
  - Generation of non-decay-corrected TACs from [Ga]-NeoBOMB1 PET/CT images in normal organs, tumour lesions
  - Calculation of residence times in organs and tumour lesions of [Ga]-NeoBOMB1
  - Calculation of absorbed doses and effective whole body dose of [Ga]-NeoBOMB1
  - Calculation of the SUV of each lesion
  - Number and location of tumour lesion detected by [Ga]-NeoBOMB1 in comparison with comparable standard imaging modalities such as FDG-PET

- Calculation of the [Ga]-NeoBOMB1 PET overall, positive and negative agreement on a lesion-by-lesion basis as well as on a patient basis relative to the standard imaging overall and for each tumour type
- Comparison of number of patients with tumour lesions detected and number of tumour lesions detected by [Ga]-NeoBOMB1 with cytology and/or histopathology from archival and/or recent biopsy specimens
- Calculation of the [Ga]-NeoBOMB1 PET sensitivity and specificity on a lesion-bylesion basis for all lesions with associated biopsy data, and on a patient basis relative to histopathology / cytology data

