## 4.1.3 Vital signs

Vital signs will be measured at all visits except at Day 2 for patients included in the nondosimetry group.

On injection/PET day, i.e. Day 1, vital signs will be recorded

- at pre-dose, immediately after radiotracer injection, 30 min p.i. and after the last image acquisition (about 4h) among patients of the **dosimetry group**.
- at pre-dose, 30 min p.i. among patients of the **non-dosimetry group.**

Heart rate and blood pressure will be measured after patient has been in a seating position for 5 minutes.

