#### **4** ANALYSIS POPULATIONS

#### 4.1 Full Analysis Set

The Full Analysis Set (FAS) will consist of all patients who enter the study and receive the [Ga]-NeoBOMB1 dose. The safety set in this case is identical to the FAS and so will not be defined as a separate set.

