#### 8.3 Vital Signs

Descriptive statistics will be provided for the vital signs measurements (systolic blood pressure, diastolic blood pressure and heart rate) and changes from baseline, if available, at each scheduled visit. The minimum post-baseline value, maximum post-baseline value, and last post-baseline value will be summarized in the same manner, where both scheduled and unscheduled post-baseline values will be included for deriving the minimum/maximum/last post-baseline value.

Vital signs results will also be presented graphically in terms of box plots of absolute values over time and changes from baseline over time.

All vital sign measurements will be listed by subject at each scheduled visit.

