#### 8.4 ECG Parameters

Electrocardiogram parameters (PR, RR, QRS, QT, QTcF, and QTcB) will be summarized using descriptive statistics for actual values and for change from baseline at each scheduled visit. The minimum post-baseline, maximum post-baseline, and last post-baseline value will be summarized in the same manner, where both scheduled and unscheduled post-baseline measurements will be considered for deriving the minimum/maximum/last post-baseline value.

Note that Frederica's and Bazett's correction to the reported QT interval, QTcF and QTcB, respectively, will be derived (in milliseconds) for all subjects and time points as follows:

QTcF (msec) = 
$$\frac{QT(msec)}{\sqrt[3]{RR(msec)/1000}}$$
; QTcB (msec) =  $\frac{QT(msec)}{\sqrt{RR(msec)/1000}}$ 

The number and percentage of subjects with elevated QTcF and QTcB during the post-baseline period will be presented for the following categories: QTcF or QTcB worsening to >450 msec, >480 msec, and >500 msec from baseline, and increase in QTcF or QTcB from baseline >30 msec and >60 msec.

Overall interpretations of ECG assessment will be tabulated by the number and percentage of subjects in each category (normal, abnormal but not clinically significant, abnormal and clinically significant, not evaluable, or unknown) at each visit and at worst post-baseline assessment.

Electrocardiogram parameters results will also be presented graphically in terms of box plots of absolute values over time and changes from baseline over time.

All ECG measurements and overall interpretation will be listed by subject.

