#### **10 SAMPLE SIZE AND POWER CONSIDERATIONS**

The primary objective of the trial is to assess preliminary targeting properties of [Ga]-NeoBOMB1. Data for this objective will be reported descriptively therefore no formal statistical sample size calculation is feasible. It is anticipated that 50 patients with malignancies known or suspected to overexpress GRPR will be recruited in the trial and will be administered [Ga]-NeoBOMB1 prior to PET-CT imaging. According to histopathology data, a great percentage of these patients is expected to be GRPR positive. However, some patients will also be recruited whose tumors do not show GRPR positive expression by histopathology/cytology data. This will allow calculation of preliminary diagnostic characteristics and the sample size should allow reasonable precision around estimations of targeting properties. For instance, if a patient level sensitivity of 83.3% is observed (for e.g. if 25 patients had lesions detected by [Ga]-NeoBOMB1 imaging out of 30 patients in the trial with GRPR positive histopathology/cytology) the 95% CI around this would be 66.4% to 92.7%.

The overall sample size of 50 patients will be fixed to ensure 10 patients are recruited within each of the tumor types included in the trial. Although it won't be possible to make strong conclusions within the tumor types, this should ensure that a reasonable number of GRPR positive patients are available within each tumor type and this will allow initial estimates of diagnostic properties to be made and will ensure each tumor type is fairly represented.

Ten patients will be recruited to the dosimetry sub-population of the trial. This is considered sufficient to obtain data on dosimetry, bio-distribution and dose-limiting critical organs. Data from all 50 patients in the trial will be used to assess all other study objectives.

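### Tolerability is defined by the absence of clinically relevant changes in blood pressure, heart rate and ECG; it should be a patient count with a confidence interval, and SAP 8.3 has no such count for vital signs.

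*SAP*

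**What the plan says.** SAP 3.2 describes the tolerability and safety of a diagnostic dose "in patients with malignancies known to overexpress GRPR as determined by absence of" two things. One is an excess of SAEs over other peptide-based radiotracers, which is not at issue here. The other is "clinically relevant changes of physiological parameters (blood pressure, heart rate, and ECG findings"). Protocol 3.3.2 has the same second limb: "clinically relevant changes of physiological parameters (blood pressure, heart rate, ECG findings"). Neither place gives a threshold, a time window, an assessor, an attribution requirement or a tolerated frequency.

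The population is one arm of dosed patients. SAP 4.1 states that "The safety set in this case is identical to the FAS", and SAP 10 that "The overall sample size of 50 patients will be fixed to ensure 10 patients are recruited within each of the tumor types" studied. Baseline is the last assessment before administration (SAP 5.2).

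The analysis sections treat the three kinds of measurement differently:

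- **Vital signs (SAP 8.3):** "Descriptive statistics will be provided for the vital signs measurements" and their changes from baseline, with post-baseline extremes, box plots and listings. There is no count of patients with a relevant change.
- **ECG (SAP 8.4):** patient counts for QTc categories, including "increase in QTcF or QTcB from baseline >30 msec and >60 msec", and a table of patients by overall interpretation that separates clinically significant from non-significant abnormality.
- **Laboratory tests (SAP 8.2):** patient counts by clinical significance and shift tables by toxicity grade.

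Protocol 7.4 lists clinically significant changes in vital signs among the things on which safety is evaluated. For intervals, SAP 5 says only that they will be computed when appropriate; section 8 names none.

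**The concern.** An absence criterion with no control arm has two weaknesses. First, a single change that has nothing to do with the tracer breaks it. Such changes are plausible: Protocol 5.4 allows patients on active systemic treatment and lets chemotherapy resume 48 hours after the injection, so Day 7 and Day 14 readings can fall under other therapy. Second, when the criterion is met, absence in 50 patients may be read as showing tolerability although rates of several percent remain possible.

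Separately, the planned vital-sign tables do not yield the quantity that the endpoint names. Means, extremes and box plots do not show how many patients had a clinically relevant change in blood pressure or heart rate. With *clinically relevant* undefined, that judgement could be made after the data have been seen.

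What is at stake is the wording of the safety conclusion: a bare statement of absence, or a rate with its uncertainty.

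**Working it through.** **The plan's own interval.** Protocol 7.1 and SAP 10 give 25/30 = 83.3% with a 95% CI of 66.4% to 92.7%. The Wilson score method reproduces this exactly; Clopper-Pearson gives 65.3% to 94.4%. The figure concerns sensitivity. No precision figure is given for safety.

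**Inputs.** N = 50 (10 dosimetry, 40 non-dosimetry). The background rate q of clinically relevant changes per patient is not in the documents and is assumed over a range.

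**Probability that background alone breaks the criterion.** With independent patients, P(at least one of 50) = 1 − (1 − q)^50, and P(none) is its complement.

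| Assumed q per patient | P(at least one) | P(none) |
|---|---|---|
| 0.5% | 22.2% | 77.8% |
| 1% | 39.5% | 60.5% |
| 2% | 63.6% | 36.4% |
| 5% | 92.3% | 7.7% |

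The 50% point is q = 1 − 0.5^(1/50) = 1.38%.

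**The same per reading occasion.** Dosimetry patients have 6 post-dose vital-sign checks. On Day 1 readings are taken "at pre-dose, immediately after radiotracer injection, 30 min p.i. and after the last image acquisition (about 4h"), so three follow the injection; Days 2, 7 and 14 add three. By the text of Protocol 4.1.3 and 4.3, non-dosimetry patients have 2 or 3 (30 minutes, Day 14, and Day 7 if it is a physical visit). The schedule in Protocol 4.5 also marks 0-5 min for them, giving up to 4.

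- 10×6 + 40×2 = 140 occasions: the 50% point is 0.49% per occasion
- 10×6 + 40×3 = 180 occasions: 0.38%
- 10×6 + 40×4 = 220 occasions: 0.31%

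These treat occasions as independent, which is a simplification. The text and the schedule disagree on the 0-5 min reading and must be reconciled.

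**What zero events would show.** The upper limit for 0/50 is 1 − 0.025^(1/50) = 7.1% (Clopper-Pearson, two-sided 95%), or 1 − 0.05^(1/50) = 5.8% (one-sided 95%). Wilson also gives 7.1%. A true 3% rate yields 0/50 with probability 0.97^50 = 21.8%.

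**What the proposed report would look like** (Clopper-Pearson 95%): 0/50 gives 0 to 7.1%; 1/50 gives 0.05% to 10.6%; 2/50 gives 0.5% to 13.7%.

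**Dependence on the event definition.** To see how far the result turns on the threshold, take independent normal QTcF readings with no drug effect, one baseline reading, and 6 post-dose readings in 10 patients and 2 or 3 in 40. The within-patient SDs are assumed. The chance that at least one patient exceeds each SAP 8.4 category is:

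| Assumed SD | Rise >30 ms | Rise >60 ms |
|---|---|---|
| 8 ms | 40-48% | about 0% |
| 10 ms | 87-92% | about 0.2% |
| 12 ms | about 99% or more | about 3-4% |

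The two categories stand in the same SAP sentence, and neither is named as the level that counts as clinically relevant.

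**The case against.** The strongest reply is that nobody will run this as a pass/fail rule. The analysis is descriptive, testing is exploratory (SAP 5), section 8 derives no yes/no tolerability result, and no trial decision depends on one. *Clinically relevant* also implies judgement: investigators review and sign every ECG (Protocol 4.1.4), so random variation across a numeric cutoff is not by itself the event. All of this stands.

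A reader might infer that a harmless tracer would usually fail the criterion, or that the criterion cannot discriminate. The documents do not support this. They give no background rate, and at 0.5% per patient or less the failure probability is 22.2% or less. Simulated failure rates depend on assumed SDs and on a cutoff that the SAP does not equate with clinical relevance; moving from >30 ms to >60 ms takes them from 40% or more down to 4% or less.

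A reader might also infer that vital-sign changes are never counted per patient. That too goes too far. The Toxicity Grading Scale grades tachycardia, bradycardia, hypertension and hypotension, and SAP 8.1 counts treatment-emergent adverse events per patient, by worst grade and by relatedness. A blood pressure or heart rate change reported as an adverse event is therefore counted. One that is not so reported would appear only in summaries and listings.

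Finally, SAP 5 permits confidence intervals. It does not require one for safety proportions, so the gap is one of specification.

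**Conclusion.** The point holds as a should-fix on wording and tabulation. The stated criterion is absence, in a single arm of 50, with no allowed background frequency or attribution. Taken literally, it is broken by one background event, with probability from 22.2% to 92.3% over assumed rates of 0.5% to 5% per patient. If it is met, it leaves true rates up to 7.1% open (two-sided 95%), a limit the SAP does not require to be reported. That limit depends only on n and assumes that all 50 patients are assessable; the failure probabilities depend on rates the documents do not supply.

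The vital-sign gap needs no assumption: Protocol 7.4 relies on clinically significant changes, SAP 8.2 and 8.4 count patients by clinical significance, and SAP 8.3 does not. SAP 11 does not list this as a departure from the protocol. The safety data will be reported either way; what changes is what may be concluded from them.

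**What to change.** 1. In Protocol 3.3.2 and SAP 3.2, replace the absence criterion for physiological parameters by the number and percentage of patients with a clinically relevant change in blood pressure, heart rate or ECG, with an exact (Clopper-Pearson) 95% CI. State that 0/50 excludes only rates above about 7%.
2. In SAP 8.3, add one patient-count table for blood pressure and heart rate, parallel to 8.2 and 8.4. Use the investigator's clinical-significance judgement if the CRF records it; otherwise use shifts from baseline to worst post-baseline grade on the Toxicity Grading Scale that the protocol already adopts.
3. Fix the event definition before database lock: how relevance is judged, the time window, and whether attribution is reported alongside.
4. Reconcile Protocol 4.1.3 and 4.1.4 with the schedule in 4.5 on the 0-5 min readings in the non-dosimetry group.

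The cost is wording in both documents and one table from readings already planned, with no new visits. The resulting claim is slightly less favourable than a statement that no changes occurred.

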#### **4** ANALYSIS POPULATIONS

#### 4.1 Full Analysis Set

The Full Analysis Set (FAS) will consist of all patients who enter the study and receive the [Ga]-NeoBOMB1 dose. The safety set in this case is identical to the FAS and so will not be defined as a separate set.

#### 4.2 Per Protocol Set

The Per Protocol (PP) Set consists of all patients of the FAS who complete the study according to the protocol with no major protocol violations (i.e. CSR reportable violations as specified in the Protocol Deviation Plan).

The list of subjects to be excluded from the PP Set will be finalized prior to database lock.

All analyses will primarily be performed on the FAS, and selected analyses may be repeated on the PP Set if there are sufficient number of violations to warrant it. Deviation of results by using the PP Set will be discussed.

#### 5 GENERAL CONSIDERATIONS FOR DATA ANALYSIS

The primary focus of the statistical analysis will be on descriptive statistics and graphical presentations of data. Continuous variables will be presented as numbers of non-missing values, mean, standard deviation, median, minimum, maximum and quartiles. For categorical variables, descriptive statistics will include counts and percentages per category. Confidence intervals will be computed when appropriate. Continuous variables will be compared where relevant (by point estimates and confidence intervals) using the most appropriate approach such as paired analysis Mann-Whitney-Wilcoxon U statistic or paired analysis Student's *t* statistic. Proportions will be compared using the appropriate test statistic among Chi-squared test statistic, Fisher exact test statistic or McNemar test statistic. Point estimates and confidence intervals will also be computed when feasible. Pearson's or Spearman linear regression analysis will be used to explore potential relationships between two continuous variables as appropriate. Any hypothesis testing that is performed will be interpreted as exploratory and no emphasis will be placed on nominal significance levels.

All analyses will be performed using SAS® Version 9.3 or later (SAS Institute Inc., Cary NC).

All data presentations will be presented primarily by the overall population but may also be repeated split by tumor type where relevant. Some presentations will also be repeated split by whether or not the patient was found to have tumors bearing GRPR expression according to cytology and/or histopathology findings.

